During FY 2012, 391 patients with implanted port catheters were treated in the OPCC. Seventy of these patients experienced an occlusion of their port that required the administration of alteplase (CathFlo) ([name], personal communication, October 12, 2012). Thus, 70 of 391 experienced an occlusion resulting in an occlusion rate of 18%. Some of these 70 patients experienced an occlusion more than once during that time. Additionally, during that time, a few patients had their implanted port catheters removed due to infection or malfunction. The exact number of patients who experienced multiple occlusions or had their implanted ports removed/replaced during FY2012 is unknown.

During the planning of the current study evaluating implanted port catheters, we engaged the consultation of a biostatistician through the Center for Clinical and Translational Science and Training (CCTST) to conduct a power analysis to

establish the number of participants needed in each group to determine the non-inferiority of the alternative therapy (saline only flush). Consultation was provided by [name], Associate [name] Hospital Medical Center, University of Cincinnati.

Based on the literature and our own experience we estimated an approximate occlusion rate of 20% with the standard treatment (saline + heparinized saline flush as described above). The power analysis conducted by [name] determined that, using a two group normal approximation test of proportions with a one-sided .05 significance level, a sample size of 198 participants per group will have 80% power to reject the null hypothesis that the proposed method is not inferior (i.e. the difference in proportions between the proposed method and the standard method is greater than 0.10). Thus, we will continue to recruit participants in that study until 198 have been enrolled in each group for a total of 396 study participants.

[name] was consulted again when the introduction of the BioFlo Port at TriHealth was discovered. It is [name] recommendation that this second randomized controlled trial using the same methodology and power analysis calculations be conducted. Thus, we will recruit 198 participants per group for a total of 396 participants in this study.

Data Collection:

Independent Variables: Method for flushing implanted port catheters:

- 20 mL of saline followed by 5 mL of Heparinized saline in a concentration of 100 units/mL
OR
- 20 mL of saline only

Dependent Variables:

Primary Outcomes

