- Occurrence of first complete (can neither withdraw blood nor flush the catheter) occlusion
- Occurrence of first partial (able to flush but unable to withdraw blood) occlusion
- Frequency with which alteplase (CathFlo) has to be utilized to resolve an occlusion

Secondary Outcomes

- Number of subsequent occurrences of complete or partial occlusions after the first occurrence.
- Amount of time in days that a port remains patent (flushes easily and able to obtain a blood return).
 - Amount of time between entrance in study and first incidence of partial or complete occlusion

- Amount of time between incidences of partial or complete occlusion.
- Occurrence of other complications:
 - Central Line-Associated Blood Stream Infection (CLABSI) – a laboratory-confirmed (recognized pathogen cultured from one or more blood cultures; organism cultured from blood is not related to an infection at another site) blood stream infection that is considered central line associated (CDC, 2012).
 - Develops complication related to Heparin
 - HIT (Heparin induced thrombocytopenia as measured by a positive HIT antibody test)
 - Other heparin allergy

Moderating variables: other things that could also affect patency of the port

- Number of times port flushed per month or frequency of flushing.
- Use of prophylactic doses of anticoagulant drugs (e.g., enoxaparin, heparin, warfarin)
- Development of a hypercoaguable state, as diagnosed by primary hematologist/oncologist
- Mechanical difficulties related to port placement e.g. “Pinch-off syndrome”
- Length of time port has been in place prior to entrance in study

Extraneous variables:

- Type of cancer
- Age of participant

Data collection tool

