The data collection tool (see Implanted Port Catheter Flushing Data Collection Form – Face Sheet: Appendix C and Record of Flushes: Appendix D) were developed by the principal and sub-investigators specifically for the purpose of this study. The tool was reviewed by the OPCC nurses for completeness and clarity. In addition to basic demographic information (age, gender), the nurse will record the patient's type of cancer, and the diagnosis or history of any hypercoaguable state or use of anticoagulant medication as documented in the patient chart. The nurse will also document the type of implanted port catheter (single/double), the port location (right/left, subclavian vein (described in the operative note or chest x-ray), and the date the port was inserted so that length of time the port has been in place can be calculated. Data will be recorded on the Face Sheet when the patient is enrolled in the study and as pertinent information/events become known, i.e., as complications occur.

With each visit to the identified treatment center, the nurse will document the date and characteristics related to the patency of the port catheter on

the Record of Flushes data collection tool. In the event the blood withdrawal is sluggish or absent, the patient will receive a dose of alteplase (CathFlo) according to the TriHealth Nursing Policy: VAD: Care & Maintenance (Appendix A) and as ordered by the physician. Dosage and results of that intervention will also be recorded on the Record of Flushes data collection tool. In the event that any study participant (regardless of group assignment) requires alteplase (CathFlo) on three (3) consecutive visits to the treatment center, the patient's participation in the study will be terminated and they will be excluded from further data collection. The patient will be returned to a standard maintenance protocol for flushing of the port as prescribed by the afore-mentioned TriHealth Nursing policy (see Appendix A) or as prescribed by attending physician.

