Potential risks for study participants in either arm of the study include partial occlusion (can instill flush solution but not withdraw blood) and complete occlusion (can neither instill flush solution nor withdraw blood). Study participants could require removal of the port if an occlusion cannot be resolved, and possibly require re-insertion of a new implanted port. In the event of any occlusion, alteplase (CathFlo) in the policy established dose and frequency (see Appendix A) will be instilled to resolve the occlusion. Study participants whose implanted ports are found occluded on three (3) consecutive visits to the treatment center will be excluded from further data collection, i.e., their participation in the study will be terminated. The standard flushing as prescribed by the TriHealth Nursing Policy (see Appendix A) or as prescribed by the attending physician will be used. Study participants whose occlusion cannot be resolved with alteplase and require removal of the port will also be terminated and excluded from further data collection. Patients who develop port infections necessitating port removal will be terminated and excluded from further data collection. Study participants who develop HIT (heparin induced thrombocytopenia) or other heparin allergy will be terminated and excluded from further data collection. Likewise, patients who have thrombotic or embolic phenomenon requiring therapeutic anticoagulation will be terminated and excluded from further data collection.

The study will be closed if there is evidence that study participants in the intervention arm experience implanted port occlusion at a disproportionate rate. The amount of alteplase (CathFlo) used in each group will be assessed each month for monitoring purposes.

The undertaking of this research does require the participation of other personnel, facilities or departments other than those used in data collection. In the event the study participant is admitted to the hospital or requires some intervention using their implanted port catheter (e.g., CT scan with contrast), the study participant will have an information card describing his/her participation in the study and the group to which he/she has been randomized, so that the assigned flush solution is used, and integrity of the study can be maintained. The study participant will receive the card with instructions at the time of his/her enrollment in the study (see Appendix E Wallet Study Card).

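### Occlusions and alteplase use are systematically recorded only at infusion-center visits; events found and cleared during admissions or imaging may be missed, which could favor non-inferiority if saline is truly worse.

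*Combined protocol and SAP*

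**What the plan says.** All references are to the combined protocol and SAP.

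- **Primary Outcomes** lists first complete occlusion, first partial occlusion, and "Frequency with which alteplase (CathFlo) has to be utilized to resolve an occlusion".
- **Data collection tool** sets the routine record: "With each visit to the identified treatment center, the nurse will document the date and characteristics related to the patency of the port catheter". This goes on the Record of Flushes, as do alteplase dosage and result. The same section has the Face Sheet completed at enrollment and updated when relevant events come to light.
- **Experimental Aspect of the Study** expects the port to be used elsewhere. It covers the case "In the event the study participant is admitted to the hospital or requires some intervention using their implanted port catheter (e.g., CT scan with contrast" and so on, and describes the departments involved as separate from those collecting data. The link it describes is a wallet card, whose stated purpose is that the assigned flush is given.
- The paragraphs just before that section's heading keep the Face Sheet and the current Record of Flushes in the patient folder at the treatment center.
- **Recruitment** gives the design. The calculation is described as "using a two group normal approximation test of proportions with a one-sided .05 significance level". The target is 198 per group for 80% power. The planning assumption is stated as "we estimated an approximate occlusion rate of 20% with the standard treatment", and the null hypothesis is that "the difference in proportions between the proposed method and the standard method is greater than 0.10".

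**The concern.** The plan protects which flush is given outside the infusion centers, but describes no return of outcome data from there. Suppose a port is found occluded on a ward and cleared with alteplase. At the next center visit it flushes and draws normally, and the nurse correctly records it as patent. Unless someone mentions the event, the first occlusion and the alteplase use are not counted, and time to first occlusion is overstated.

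In a non-inferiority trial this loss is not automatically conservative. The margin is a fixed absolute difference. Missing a similar share of events in both arms scales down a real excess on saline but leaves the margin where it is. At stake is the chance of declaring saline non-inferior when its occlusion rate is really 10 points higher.

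**Working it through.** **Inputs from the plan (Recruitment):** control rate 20%, margin 0.10 absolute, one-sided alpha 0.05, 198 per group, 80% power.

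**Input not in the plan:** m, the fraction of participants with an occlusion whose event never reaches the data. It is assumed here and varied from 0 to 20%.

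**Step 1: reproduce the design.** With equal true rates of 20% and the unpooled normal approximation,

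n = (1.645 + 0.842)² × (0.20×0.80 + 0.20×0.80) / 0.10² = 197.8, rounded up to 198 per group.

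This matches the plan. Power at 198 is 80.0%.

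**Step 2: same m in both arms, true difference at the margin (20% vs 30%).** Each observed rate is the true rate × (1 − m). The chance of declaring non-inferiority is

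P = Φ((0.10 − d)/SE − 1.645), where d is the observed difference and SE = √[(p₁(1−p₁) + p₂(1−p₂))/198].

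| m | observed rates | d | SE | (0.10 − d)/SE | P (false claim) |
|---|---|---|---|---|---|
| 0 | 20% vs 30% | 0.100 | 0.0432 | 0 | 5.0% |
| 2% | 19.6% vs 29.4% | 0.098 | 0.0429 | 0.047 | 5.5% |
| 5% | 19% vs 28.5% | 0.095 | 0.0425 | 0.118 | 6.3% |
| 10% | 18% vs 27% | 0.090 | 0.0417 | 0.240 | 8.0% |
| 20% | 16% vs 24% | 0.080 | 0.0400 | 0.500 | 12.6% |

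Simulation of 1,000,000 trials at each of m = 0, 10 and 20% gave 5.0%, 8.0% and 12.6%.

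**Step 3: smaller true differences, same m in both arms.** With a true excess of 5 points (20% vs 25%), the chance of declaring non-inferiority goes from 32.6% to 38.9% (m = 10%) and 46.5% (m = 20%). With no true difference, the expected difference stays at zero. Only the variance falls, and power rises from 80.0% to 82.8% and 85.8%.

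**Step 4: different m by arm, true rates 20% vs 30%.**

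- 20% of control and 10% of saline events missed: observed 16% vs 27%, d = 0.11, SE = 0.0409, P = Φ(−0.244 − 1.645) = 2.9%.
- 10% of control and 20% of saline events missed: observed 18% vs 24%, d = 0.06, SE = 0.0408, P = Φ(0.980 − 1.645) = 25.3%.

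The direction therefore depends on which arm loses more.

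**The case against.** The strongest reply is that the plan has other routes by which off-site events can enter the data.

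- **Face Sheet.** It is updated as complications come to light, and the Purpose of Study section counts partial or complete obstruction among possible complications. This stands against any claim that recording happens only at visits. But the route is passive: no source, question, search or responsible person is named.
- **Enrollment log (Privacy Information).** It links study code to medical record number so that missing data can be checked. A cleared off-site occlusion leaves no blank field to prompt a check.
- **Monthly alteplase review by group.** Its data source is not stated, and its stated purpose is monitoring.
- **Unseen appendices.** Appendices A and C to E (nursing policy, both forms, wallet card) were not available. They may contain a field or instruction that closes the gap. This stands as a limit on the point.

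A second reply is that the assumed fractions may be generous. Participants are on active treatment and receive routine port care at the centers. For the yes/no outcome, an event is lost only if it is found and cleared elsewhere, never comes to light, and no later occlusion is seen at a center. The Recruitment section notes that some patients occlude more than once. This also stands, and is why the range starts at 2%.

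A third reply is about scale. The 18% (70 of 391) quoted alongside the 20% planning rate comes from patients treated in one center. If it was ascertained there, which is not stated, 20% may already be an observed rate. That changes little: observed rates of 20% vs 29% (m = 10%) give SE 0.0430 and P = Φ(0.233 − 1.645) = 7.9%, and 20% vs 28% (m = 20%) give SE 0.0427 and P = Φ(0.468 − 1.645) = 12.0%. It also stands that the calculation uses one combined occlusion proportion. The plan lists complete and partial occlusion separately, and alteplase frequency is a count to which the 0.10 margin does not directly apply.

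**Conclusion.** The concern holds in a limited form. The available text describes systematic recording at infusion-center visits only, while expecting port use by departments outside data collection. Following the plan as written can therefore undercount primary-outcome events. If saline is truly 10 points worse and capture is similar in both arms, the false non-inferiority rate rises from 5.0% to between 5.5% and 12.6% over an assumed 2 to 20% missed.

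A reader might infer more than this, and the documents do not support it:

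- *That off-site events are certain to be lost.* Some will come to light through the Face Sheet, and an uncleared or recurrent occlusion would be found at a later visit.
- *That the bias always favors saline.* With no true difference nothing shrinks. Assignment is open (colored stickers, a wallet card stating the group), so capture could differ by arm; the two unequal cases above give 2.9% and 25.3%.
- *That the sample size is wrong.* The figure of 198 per group reproduces.
- *That the size of the effect is known.* The documents give no share of occlusions found off-site.

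The change is worth making because it is cheap and the potential error concerns the primary outcomes.

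**What to change.** Add to Data collection tool that, at study exit or month 12, existing study staff search each participant's TriHealth EPIC record over the participation period for catheter-clearance alteplase and for notes of port occlusion or port removal. Specify that:

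- the occlusion definitions under Primary Outcomes are applied identically in both arms;
- events are classified without knowledge of assignment where feasible, since an open search could itself create unequal capture;
- events not already recorded are added, with date and location, to the primary outcome counts;
- the analysis is reported with and without the added events.

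If an appendix already provides for this, a cross-reference in the main text would show it.

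The cost is one record search per participant (396 in total) and a short protocol addition. EPIC already holds the consent documentation, and the enrollment log links study codes to record numbers. Flushing, clinical care and sample size do not change. Events treated outside TriHealth would still be missed, and the report should say so.

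### Alteplase is given for sluggish as well as absent blood return, but occlusion means absent return only, so a port can be treated at three visits and leave the study with no event in the non-inferiority test

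*Combined protocol and SAP*

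**What the plan says.** **Treatment and exit (Data collection tool).** Alteplase has two triggers: "In the event the blood withdrawal is sluggish or absent, the patient will receive a dose of alteplase (CathFlo"). A participant who "requires alteplase (CathFlo) on three (3) consecutive visits to the treatment center" is terminated from the study. The visit record is broad: "With each visit to the identified treatment center, the nurse will document the date and characteristics related to the patency of the port catheter". Alteplase dose and result are recorded as well.

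**Outcomes (Primary Outcomes).** Complete occlusion means that the port neither flushes nor gives blood. The partial form is "Occurrence of first partial (able to flush but unable to withdraw blood) occlusion". A third primary outcome is "Frequency with which alteplase (CathFlo) has to be utilized to resolve an occlusion". Sluggish return is in neither occlusion definition.

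**Patency (Secondary Outcomes).** One outcome is "Amount of time in days that a port remains patent (flushes easily and able to obtain a blood return"). Slow return is not addressed there either.

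**Risk paragraphs (Experimental Aspect of the Study).** The definitions are repeated as "partial occlusion (can instill flush solution but not withdraw blood) and complete occlusion (can neither instill flush solution nor withdraw blood"). Treatment is tied to occlusion: "In the event of any occlusion, alteplase (CathFlo) in the policy established dose and frequency" is to be instilled. What appears to be the same three-visit exit is worded here as a port being occluded at three visits in a row, not as alteplase being needed at three visits in a row.

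**Test (Null Hypothesis; power analysis under Recruitment).** The hypothesis and the 10% margin concern the occlusion rate. The planning rate is 20%, with 198 per group, one-sided 0.05 and 80% power. The historical rate behind it is 70 of 391 patients whose occlusion needed alteplase.

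**The concern.** The treatment trigger is wider than the event definition, and the exit rule is tied to treatment in one place and to occlusion in another. Under the stated definitions these are different events. A participant whose return is sluggish but never absent can receive alteplase at three consecutive visits, be withdrawn for a failing port, and contribute a non-event to the primary comparison. Any earlier visit with absent return would still count.

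If treated sluggish return is more common on saline-only flushing, leaving it out lowers the saline occlusion rate relative to heparin and favours a non-inferiority claim. If it is equally common in percentage points, nothing changes. If it is more common on heparin, the effect reverses. Because the supplied text supports two event counts, the choice between them could be made after the data are seen.

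**Working it through.** **1. The two readings side by side.**
- *Every alteplase-treated port is occluded.* In favour: the historical count under Recruitment is of occlusions needing alteplase; the third primary outcome links alteplase to resolving an occlusion; the risk paragraph pairs alteplase with any occlusion and words the exit by occlusion.
- *The outcome definitions apply as written.* In favour: both definitions, given twice, require that blood cannot be withdrawn, and the patency outcome asks only that a blood return can be obtained. A sluggish port gives some blood.

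No sentence chooses between them, and the protocol does not say whether sluggish-only ports were among the 70 of 391 (17.9%).

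**2. The plan's own figure.** Inputs from the power analysis: 20% in both arms, margin 0.10, one-sided 0.05 (z = 1.645), 80% power (z = 0.842).

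n = (1.645 + 0.842)² × 2 × 0.20 × 0.80 / 0.10² = 197.8, so 198 per group. The stated size reproduces.

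**3. Formula for the rest.** With n = 198 per group and counted rates pC (heparin) and pS (saline):

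SE = √[pC(1 − pC)/n + pS(1 − pS)/n]

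P(claim) = Φ[(0.10 − (pS − pC))/SE − 1.645]

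Check at 20% against 20%: SE = 0.0402, 0.10/0.0402 = 2.487, Φ(0.842) = 80.0%.

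**4. What leaving out sluggish-only cases could do (hypothetical).** The documents give no sluggish-only rate. Assume that the target is any alteplase-treated dysfunction and that its true rates are 20% (heparin) and 30% (saline), exactly at the margin. One percentage point is about 2 of 198 participants.

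| Uncounted sluggish-only cases | Counted, heparin vs saline | Chance of a false claim |
|---|---|---|
| Equal, 2 points each | 18% vs 28% | 5.0% |
| Equal, 5 points each | 15% vs 25% | 5.0% |
| Saline higher by 1 point | 18% vs 27% | 8.0% |
| Saline higher by 2 points | 18% vs 26% | 12.3% |
| Saline higher by 3 points | 18% vs 25% | 18.0% |
| Heparin higher by 1 point | 17% vs 28% | 3.0% |

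Worked line for 18% vs 26%: SE = 0.0414, (0.10 − 0.08)/0.0414 = 0.483, Φ(0.483 − 1.645) = 12.3%. Exact binomial enumeration of the same rule gives the same values. Only the between-arm difference in the uncounted cases matters appreciably. If occlusion as strictly defined is the target, the test stays at 5%.

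**5. Effect of counting more events, same rate in both arms.**

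| Event rate | Power at 198 per group | n per group for 80% |
|---|---|---|
| 20% | 80.0% | 198 |
| 21% | 78.8% | 206 |
| 22% | 77.5% | 213 |
| 25% | 74.3% | 232 |
| 30% | 70.1% | 260 |

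**6. Effect of unblinded calling of sluggish return.** Folder stickers and face-sheet colours show the group. If the judgement enters the tested event, over-calling by 2 points on saline with equal true rates (20% vs 22% counted) cuts power to 62.2%. Under-calling by 2 points on saline at a true 20% vs 30% (20% vs 28% counted) gives a 12.0% chance of a false claim.

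**The case against.** The strongest reply is that the authors plainly think of alteplase use and occlusion as the same thing. The historical rate, the third primary outcome and the risk paragraph all link the two. On that reading the uncounted exit cannot occur. This is the better supported account of what was meant, but it remains an inference: the only definitions given exclude sluggish return.

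Second, Appendix A (nursing policy) and Appendix D (flush record) are not in the supplied text and may say how sluggish return is judged and coded. That stands, so the point is not that a criterion for sluggishness is absent. A code on a form would still not settle whether the case counts in the non-inferiority test.

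Third, alteplase frequency is a primary outcome, group differences on the outcomes are to be tested, and alteplase use by group is assessed monthly. An excess on saline might therefore be seen. This is partial cover: that outcome has no margin and is worded around resolving an occlusion, so sluggish-only doses may fall outside it.

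Fourth, a strict endpoint is a legitimate choice and is less open to unblinded judgement. This stands, and it argues against making all treated sluggish return the primary event. It also means that counting three-visit exits while leaving the strict definition unamended would create an unstated hybrid, so the definition itself has to be changed.

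A reader might infer from the 8–18% figures that the trial's type I error is inflated. The documents do not support that. The figures need a target that the protocol does not state and a between-arm difference that it does not give.

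**Conclusion.** The inconsistency is real and lies between rules that the protocol states: the trigger, the event definition and the two wordings of one exit do not agree. Followed literally, a participant can be treated three times, be withdrawn for port dysfunction and carry no event into the main comparison. It should be fixed.

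Its effect cannot be sized. How often sluggish-only exits occur is unknown, as is the arm in which they would be commoner. The false-claim figures (3% to 18%) depend wholly on taking alteplase-treated dysfunction as the target and on the assumed difference between arms. It would go too far to say that the plan is biased towards non-inferiority, or that sluggish ports will certainly go uncounted. The sample size of 198 per group is arithmetically correct for its stated inputs and is not in question.

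**What to change.** 1. **One exit rule, counted as an event.** Use the same wording under Data collection tool and in the risk paragraph: alteplase required at three consecutive visits. In line with the risk paragraph's occlusion wording, state that this exit is an occlusion event in the primary non-inferiority test. Amend the definition under Primary Outcomes so that the event reads explicitly as complete occlusion, partial occlusion, or a three-visit alteplase exit.

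2. **One supportive analysis.** Pre-specify a non-inferiority analysis with the same 10% margin in which the event is the first of complete occlusion, partial occlusion, or alteplase for sluggish or absent withdrawal. Report complete, partial and sluggish-treated components by arm.

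**Cost.** No new data are needed, since patency characteristics and alteplase dose and result are already recorded at each visit. If the exits add 1 to 2 points to a 20% rate in both arms, power falls from 80% to about 79% to 78% at 198 per group. Through those exits, some unblinded judgement of sluggish return enters the primary event. The supportive analysis has about 74% to 70% power if its event rate is 25% to 30%, and it rests more heavily on that judgement, which is why it is supportive and not primary.

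### The three-consecutive-visit exit ends data collection on ports that can stay in use, so alteplase and repeat-occlusion counts are cut off by the outcome itself; the size is unknown and the main occlusion proportion is unaffected

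*Combined protocol and SAP*

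**What the plan says.** Under Dependent Variables, the primary outcomes are first complete occlusion, first partial occlusion and "Frequency with which alteplase (CathFlo) has to be utilized to resolve an occlusion". The secondary outcomes include "Number of subsequent occurrences of complete or partial occlusions after the first occurrence" and the time between occlusions.

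Two sections set the exit:

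- **Data collection tool.** It applies to any participant, in either group, who "requires alteplase (CathFlo) on three (3) consecutive visits to the treatment center". Then "the patient's participation in the study will be terminated and they will be excluded from further data collection", and "The patient will be returned to a standard maintenance protocol for flushing of the port" under the nursing policy or as the physician prescribes.
- **Experimental Aspect of the Study.** The trigger is occlusion rather than alteplase: "Study participants whose implanted ports are found occluded on three (3) consecutive visits to the treatment center will be excluded from further data collection".

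Port removal is a separate exit: "Study participants whose occlusion cannot be resolved with alteplase and require removal of the port will also be terminated". The three-visit exit therefore covers ports that can remain implanted and in use. A further exit reads: "Study participants who develop HIT (heparin induced thrombocytopenia) or other heparin allergy will be terminated and excluded from further data collection".

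Nothing provides for recording after any of these exits. Statistical Analysis names a t-test, chi-square or Fisher's exact test for group differences, and mentions neither time at risk nor early exit.

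**The concern.** The plan treats leaving the assigned flush as leaving the study. A port that fails on its first three visits is frozen at three alteplase uses, while a port with five scattered failures scores five. The ports with the most to contribute to the count outcomes are the ones that stop being counted. A treatment switch does not fully explain the stop either: a control participant sent back to the policy flush returns to the saline-plus-heparin flush already assigned.

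If one flush leaves more ports persistently failing, that arm loses more events and the difference in counts shrinks. In a trial that hopes to show comparability, this is the convenient direction. Separately, a port that exits after three partial occlusions can no longer record a first complete occlusion, which is listed as its own primary outcome. The monthly check of alteplase by group would, as far as the protocol shows, rest on the same truncated records.

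HIT and heparin-allergy exits are expected mainly in the heparin arm. Complications after them go unrecorded, although the background section describes serious consequences of HIT.

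**Working it through.** **1. The plan's own figure.** From the sample-size text under Recruitment: 20% occlusion (assumed equal in both arms), margin 0.10, one-sided 0.05, 80% power.

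n = (1.645 + 0.842)² × (0.2×0.8 + 0.2×0.8) / 0.10² = 197.8, so 198 per group. It reproduces. It is built on the proportion with an occlusion, not on counts.

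**2. Illustration of the exit rule.** The protocol gives no visit frequency and says the number with multiple occlusions in FY 2012 is unknown, so every input here is assumed:

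- persistent ports: 5% of the heparin arm, 10% of the saline arm, with chance p of alteplase at each visit;
- other ports: 0.008 per visit;
- V visits in 12 months: 12, 17 or 26;
- risk unchanged after exit.

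Difference in mean uses with full recording: 0.05 × V × (p − 0.008).

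Difference recorded under the rule: 0.05 × (p × M − 0.008 × V). M is the expected number of visits recorded for a persistent port, up to the third consecutive alteplase visit or V, found by recursion on the current run (0, 1 or 2). Exit of other ports is negligible.

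- V = 17, p = 0.5: full 0.05 × 17 × 0.492 = 0.418. M = 10.59, so recorded 0.05 × (5.296 − 0.136) = 0.258. Loss 1 − 0.258/0.418 = 38%.
- V = 26, p = 0.5: full 0.05 × 26 × 0.492 = 0.640. M = 12.40, so recorded 0.05 × (6.198 − 0.208) = 0.300. Loss 53%.

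Share of the count difference lost:

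| Visits | p=0.1 | 0.2 | 0.3 | 0.5 | 0.7 |
|---|---|---|---|---|---|
| 12 | 0.4% | 2.6% | 8% | 27% | 51% |
| 17 | 0.6% | 4.2% | 12% | 38% | 64% |
| 26 | 1.0% | 7.0% | 19% | 53% | 76% |

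At 26 visits, raising p from 0.5 to 0.7 raises the full difference from 0.640 to 0.900 but lowers the recorded one from 0.300 to 0.212.

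**3. A different model.** A simulation set 20% vs 30% of patients with any event, a continuous spread of port risk and varying chances of a repeat at the next visit. The rule kept 35% to 100% of the count difference. In a middle case (17 visits) 5.9% vs 10.3% of patients exited and a difference of 0.435 was recorded as 0.325 (75% kept). With weak clustering almost nothing was lost.

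**4. If the excess saline-arm ports recover after exit.** Suppose the extra 5% drop to 0.008 per visit once off saline. The 5% common to both arms cancel.

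- V = 17: full follow-up gives 0.05 × (5.296 + 6.41 × 0.008 − 0.136) = 0.261, against 0.258 under the rule.
- V = 26: 0.05 × (6.198 + 13.60 × 0.008 − 0.208) = 0.305, against 0.300.

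Full follow-up then recovers almost nothing.

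**5. Proportion with any event.** At V = 17, p = 0.5:

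- heparin: 0.05 × (1 − 0.5¹⁷) + 0.95 × (1 − 0.992¹⁷) = 17.1%;
- saline: 0.10 × (1 − 0.5¹⁷) + 0.90 × (1 − 0.992¹⁷) = 21.5%.

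Both are the same with and without the rule, because anyone who exits already has an event.

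**The case against.** A reader might infer that the trial's non-inferiority conclusion is biased. The documents do not support that. The hypotheses and the power calculation concern an occlusion rate with a 0.10 margin, and step 5 shows that proportion unchanged. The counts have no margin and no power calculation. This objection stands.

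A reader might also take the 38% or 53% loss as an estimate. It is not one. Those figures need persistent ports that fail on half of their visits and go on failing after they leave saline. At 10-20% per visit the loss is 7% or less, and step 4 shows it can vanish. That one arm loses more is an inference from the trigger being the outcome, not something the protocol states.

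Full follow-up has its own weakness: after exit, saline-arm ports may be flushed with heparin, and mixing solutions can itself dilute a non-inferiority comparison. That also stands, and it is why the fix asks for two counts.

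For HIT, it is tempting to multiply the background's 1-5% by 198 and call the resulting 2 to 10 control participants a bias. That incidence is for heparin exposure in general. Known heparin antibody or allergy is excluded at entry, prophylactic heparin is possible in either arm, and HIT itself is recorded before exit. What remains is only that later complications are not captured.

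**Conclusion.** The concern holds for the count and between-event outcomes, and for a first complete occlusion that follows three partial ones. Their recording is ended by the outcome itself, and the analysis section has nothing to handle this. If persistently failing ports are unequal between arms, the recorded difference in counts is too small. The loss ranges from negligible to about three quarters under the assumptions shown, and the protocol gives no means of placing the trial within that range.

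The any-first-occlusion comparison and the 198 per group are unaffected, provided each alteplase visit that leads to exit is counted as an occlusion, as the FY 2012 rate in the protocol does. The two exit wordings leave this less than certain, because alteplase is also given for slow blood return. This is worth correcting, but it is not a threat to the main test.

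**What to change.** In Data collection tool and in Experimental Aspect of the Study, separate stopping the assigned flush from stopping data collection.

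- While the port stays in place and the participant attends a study center and consents, keep completing the Record of Flushes to month 12. Add the date and reason for leaving the assigned flush and the flush then used. Apply the same to HIT and heparin-allergy exits.
- Report alteplase and repeat-occlusion counts by randomized group in two ways: over the full 12 months, and while on the assigned flush with exposure time. State in advance which question each answers.
- Reconcile the alteplase trigger in one section with the occlusion trigger in the other.
- Reconcile both with the sentence in Experimental Aspect of the Study that keeps participants for 12 months or until a listed risk occurs. Partial occlusion is the first risk listed, so read literally that sentence ends follow-up at the first occlusion and removes the repeat outcomes altogether.

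No change is proposed to the clinical decision on flushing after exit. The cost is protocol and consent wording plus continued use of a form that the same centers' nurses already complete at each visit. The sample size stays at 198 per group.
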